4.0 Enrollment/Randomization

Potentially eligible participants were identified through a clinical data warehouse that queried electronic medical records (EMR). We mailed letters and a study brochure to potentially eligible participants, asking that they let research staff know of their interest or to request no further contact. After one week, study staff called potential participants who did not opt-out to explain the study and assess interest. Interested participants confirmed inclusion and exclusion via self-report by phone and then completed informed consent by phone. Enrolling participants were asked if they wish to invite a support person, but support person invitation and/or enrollment was not required. Research staff obtained contact information for a potential support person. Research staff then contacted potential support persons to confirm eligibility and obtain their verbal informed consent by phone. All participants were sent a copy of the consent document.

Consented patient participants were sent a survey and A1c kit and consented support person participants were sent a survey. Once patient participants completed the survey and put their A1c kit in the mail, they were randomized. Support persons were randomized with the patient participant.

Participants (or dyads) were randomized to intervention or control with a 1:1 ratio. As baseline data were available at randomization, the study statistician performed an adaptively stratified randomization process to ensure balance between treatment arms on support person enrollment status and baseline values of outcomes of interest for the patient participant. The randomization algorithm placed relative importance on balancing specific covariates through weighting, the balance of which shifted once during enrollment in response to an imbalance in baseline variables. The statistician gave study staff randomization assignments after participant enrollment and baseline data collection were complete, blinding allocation until randomization.

Then, study staff contacted participants to tell them what to expect during their participation. This includes an overview of study components specific to their assigned condition and collection of mobile phone information and preferences for the text messaging platform.

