Harmful Involvement Perceived Criticism specific to diabetes management assessed with items from the Family Emotional Involvement and Criticism Scale with scores ranging 0 to 16 with higher scores indicating more perceived criticism related to diabetes management (worse)

Potential Moderators

Race and ethnicity Participants self-report Hispanic ethnicity and race(s)

Socioeconomic disadvantage Indicator variable calculated based on self-reported education (<12 years), health insurance (uninsured or public insurance only), or annual household income (<\$50,000 USD)

Gender Male, Female, Other self-reported gender

Cohabiting with support person Whether or not the patient participant and support person live together

Support Person (SP)

Outcomes

Diabetes Distress Family Members Problem Areas in Diabetes (PAID-FM) from the Diabetes Attitudes, Wishes, and Needs Second study (DAWN2)

FAMS 2.0 (PI: [name])
R01-DK119292
NCT04347291

with scores ranging 0-100 where higher scores indicate more distress about the PWDs' diabetes experienced by the support person (worse)
DAWN2 Family Burden Item which asks how much of a burden it is to help the PWD manage their diabetes, with responses on a scale from 0 (no burden) to 4 (a very large burden; worse)

Intervention Targets

Support Person Involvement

Helpful Involvement Family member version of the Family/friend Involvement in Adults' Diabetes (FIAD-FM) helpful scale assessing the support person's own performance of helpful behaviors over the past month with scores ranging 1 to 5 with higher scores indicating more helpful behaviors (better)

Harmful Involvement Family member version of the Family/friend Involvement in Adults' Diabetes (FIAD-FM) harmful scale assessing the support person's own performance of harmful behaviors over the past month with scores ranging 1 to 5 with higher scores indicating more harmful behaviors (worse)

Alignment between desired and actual involvement Items from the DAWN2 Family Experience of Patient Involvement measure. Scores range 0 to 4 where a score of 2 indicates alignment between the support person's current level of involvement and their desired level of involvement

Potential Moderators

Race and ethnicity Participants self-report Hispanic ethnicity and race(s)
Gender Male, Female, Other self-reported gender
Cohabiting with patient participant Whether or not the patient participant and support person live together

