8.0 Statistical Considerations

Power estimates were conservatively calculated based on a two-sample unequal variance *t*-test of 9-month A1c for a minimum detectable difference of 0.5%; we targeted enrollment of 334 dyads to obtain sufficient effective sample size to detect this effect. Allowing for a dropout rate of ~15%, an effective sample size of 284 (~142 per condition) provides 80% power to detect this minimum difference at a 5% significance

FAMS 2.0 (PI: [name])

R01-DK119292

NCT04347291

level assuming a standard deviation of 1.5%. For secondary outcomes and mediators, assuming skewness similar to A1c (in general it will be less) and retention of 80–90%, we will be able to detect standardized effect sizes of 0.32–0.34. Estimates of detectable effect were made via 40,000 simulations with a Beta distribution calibrated to approximate skewness similar to that observed in our prior work.

Our power will be greater than estimates, given our plans to use data imputation methods for missing data, and adjust for baseline values of the outcome(s) of interest and other covariates as needed per analysis, which should increase power by reducing the effective standard deviation of the outcome.

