**Version date 11/20/2023**

## Statistical Analysis Plan for NCT04347291

Our conceptual framework is shown in **Figure 1**. Outcomes include patient participants' HbA1c (primary), diabetes distress and well-being (secondary). Our intervention targets include three hypothesized mediators for patient participants: improved diabetes self-efficacy, improved diabetes self-care behaviors (i.e., dietary behavior, physical activity, and medication adherence), and improved diabetes-specific involvement from family and friends (i.e., increased helpful involvement and reduced harmful involvement). Potential moderators of patient participants' effects are gender, minority race/ethnicity, socioeconomic disadvantage, and support person cohabitation.

Primary support person outcomes are support burden and diabetes distress. Our intervention targets/hypothesized mediators for support persons are self-report on diabetes-specific support provided to the patient participant (i.e., increased involvement, increased helpful involvement and reduced harmful involvement). Exploratory analyses test if improvements in support person outcomes are mediated by improvements in patient participant outcomes (i.e., HbA1c, diabetes distress, well-being). Support person gender and cohabitation are potential moderators of support person effects.

**Figure 1. Conceptual Framework.** FAMS 2.0, Family/friend Activation to Motivate Self-Care version 2.0 evaluated in this study.

Intention-to-treat principles will be used to analyze all available data with two primary models: repeated measures regression models (generalized estimating equations; GEE) to assess main effects and subgroup effects, and structural equation modeling (SEM) techniques to test mediation. To address missing data, we use multiple imputation via chained equations with a total of M=500 iterations. One imputation model includes baseline, 6- and 9-month data during the intervention and a second imputation model includes baseline and 12- and 15-month data for sustained effects.

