To estimate FAMS' main effects and subgroup effects, we will use generalized estimating equations (GEE) with a working-independence correlation structure and identity link. Models will be adjusted for insulin use at baseline and baseline value of the outcome of interest (via a restricted cubic spline with three knots) for each model. We will allow a two-way interaction between time and condition and a two-way spline interaction between time and baseline value of the outcome. Differences between arms will be tested based on a linear combination of regression coefficients at each time point (based on Wald-based test with one degree of freedom). Point estimates and corresponding 95% confidence intervals will be obtained for each follow-up time point, to graphically display trajectories in adjusted mean outcomes difference over 15 months. We will explore subgroups effects (i.e., divided sample) to determine for whom the intervention was most or least effective using the same models as described above.

For each intervention target (**Figure 1**), we fit models as described above. Continuous measures were analyzed using the GEE model. The summative one-item physical activity measure was ordinal, and therefore analyzed using an ordinal regression model (odds ratios obtained on cumulative logit/proportional odds scale). Each model was run three times, to

estimate during (6-months), post (9-months) and sustained (15-months) intervention effects.

For mediation analyses, we model between-subjects mediation with path analysis with an SEM framework as suggested in **Figure 1**, including multiple mediators. Mediation models include intervention targets at both 6 and 9 months as mediators and a single outcome (i.e., HbA1c, diabetes distress or well-being). We ran this model separately for each outcome at 9, 12 (H1cA1c only) and 15 months. For parsimony, we restricted the number of mediators guided by findings evaluating intervention effects on these mediators, opting for continuous and sensitive mediator measure(s) of self-care behaviors unless both measures were significantly improved by the intervention. We used Amos version 29 regression imputation function to address missing data, running each imputation separately for each model.

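### Allocation was balanced on support person enrollment and several baseline outcomes, but each GEE model adjusts only for insulin use and its own baseline, so standard errors may be slightly too large

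*SAP*

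**What the plan says.** Protocol section 4.0 (Enrollment/Randomization) states that 1:1 allocation was carried out adaptively to "ensure balance between treatment arms on support person enrollment status and baseline values of outcomes of interest for the patient participant". It adds that "The randomization algorithm placed relative importance on balancing specific covariates through weighting". The section also reports that this weighting was changed one time while patients were still being recruited, after some baseline characteristics were found to differ between arms. Neither the covariates nor the weights are listed. Support person enrollment is a real variable among patients, because "support person invitation and/or enrollment was not required".

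The SAP specifies GEE with an identity link and a working-independence structure. On covariates it says: "Models will be adjusted for insulin use at baseline and baseline value of the outcome of interest". The baseline value enters as a three-knot restricted cubic spline with a time interaction. No other covariate is named.

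Protocol section 8.0 expects the analysis to "adjust for baseline values of the outcome(s) of interest and other covariates as needed per analysis" and counts on this to raise power, but does not say which other covariates. Neither document mentions a re-randomization test or any other method that takes account of the adaptive allocation.

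**The concern.** Balancing arms on a prognostic factor removes the part of the chance difference between arms that the factor would have caused. The treatment estimate then varies less than it would under simple randomization. A model that omits the factor cannot see this: the factor's variance stays in the residual, and the model-based or sandwich standard error is computed as though the arms could have differed on it. The reported standard error is then larger than the true one.

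With an identity link this does not bias the estimate, and the test rejects too seldom rather than too often. What may be lost is some precision for A1c, diabetes distress and well-being, although the variables needed to recover it were already in hand at randomization.

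The SAP does capture the largest part of the benefit, since each outcome's own baseline is likely to be its strongest predictor. What is left out is support person enrollment and the other balanced baselines. Section 4.0 speaks of baseline outcomes in the plural, so a model holding only one of them omits at least one other, for example distress and well-being in the A1c model if those were the ones balanced. Whether insulin use was a balancing factor cannot be determined.

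**Working it through.** **Inputs.** From Protocol section 8.0: difference 0.5, SD 1.5, 5% level (taken as two-sided), 80% power, 142 per arm, about 15% dropout, 334 enrolled. Assumed, because the documents give no values: q, the share of residual variance after own baseline that the omitted balancing factors explain (0 to 10%); and R², the share of outcome variance explained by own baseline (0 or 0.36).

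**The plan's own figure.** n per arm = 2 × (1.5/0.5)² × (1.960 + 0.842)² = 141.3, so 142 per arm and 284 in total. Power at 142 per arm is 80.2% (normal) or 79.9% (t). 334 × 0.85 = 283.9. The stated sample size is reproduced. It does not depend on the point made here.

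**Closed form under perfect balance (upper bounds).**

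- True SE = 1.5 × √[(1 − R²)(1 − q)] × √(2/142).
- The SAP-type model reports an SE too large by the factor 1/√(1 − q), so its effective critical value is 1.96/√(1 − q). The adjusted model uses 1.96.
- True size of the nominal 5% test = 2 × [1 − Φ(1.96/√(1 − q))].
- Power = Φ(0.5/true SE − critical value).

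Example, q = 0.05 and R² = 0: true SE = 1.5 × √0.95 × √(2/142) = 0.1735, and 0.5/0.1735 = 2.882. The SAP-type critical value is 1.96/√0.95 = 2.011. Power is Φ(0.871) = 80.8% for the SAP-type model and Φ(0.922) = 82.2% for the adjusted model.

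| q | SE excess | True size | Power, SAP-type → adjusted, R² = 0.36 | Same, R² = 0 |
|---|---|---|---|---|
| 0 | 0% | 5.0% | no change | no change |
| 0.01 | 0.5% | 4.9% | 94.1 → 94.2% | 80.3 → 80.6% |
| 0.05 | 2.6% | 4.4% | 94.4 → 95.0% | 80.8 → 82.2% |
| 0.10 | 5.4% | 3.9% | 94.9 → 95.9% | 81.5 → 84.2% |

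From the unrounded values the gains are 0.1, 0.5 and 1.0 points with R² = 0.36, and 0.3, 1.4 and 2.7 points with R² = 0.

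**Simulation with imperfect balance.** 284 patients and 20,000 runs. Biased-coin minimization (probability 0.8, equal weights) on own baseline, support person enrollment (60% assumed) and two other independent baselines. R² = 0.36, with q shared equally among the omitted factors. One follow-up contrast, a linear own-baseline term and robust SEs. Insulin use, repeated visits and imputation were not simulated. The Monte Carlo SE of the size is about 0.15 points.

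| q | Mean SE / empirical SD, SAP-type | Size, SAP-type | Size, fully adjusted | Size, no balancing factor adjusted |
|---|---|---|---|---|
| 0 | 0.996 | 5.3% | 5.2% | 1.6% |
| 0.01 | 0.994 | 5.2% | 5.3% | 1.7% |
| 0.05 | 1.023 | 4.6% | 5.2% | 1.3% |
| 0.10 | 1.048 | 4.2% | 5.2% | 1.1% |

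The last column shows how much the own-baseline term already recovers. The remaining effect is visible only from about q = 5%. Simulated power rose from 94.5% to 94.9% at q = 0.05 and from 94.5% to 95.6% at q = 0.10.

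**Second simulation, written independently.** 3,000 runs, correlated baselines, insulin use included and 70% support person enrollment assumed. With the factors omitted, mean SE / empirical SD was 1.01, 1.03 and 1.12 at q = 0, 0.05 and 0.20. With them added it was 1.01, 1.00 and 1.01. Under simple randomization the model without them gave 1.01, 1.01 and 0.98. The excess therefore comes from balancing without adjusting, not from omission alone.

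**The case against.** The strongest reply is that the SAP already deals with what matters. Own baseline is in the model, in a more flexible form than was simulated, and the simulated size under the SAP-type model stays between 4.2% and 5.3%. No document gives q, and nothing in them suggests that it reaches 5%. At q of 1% or less the simulation shows no excess. The 2.7-point gain requires own baseline to explain nothing, whereas Protocol section 8.0 expects baseline adjustment to help. The trial was sized on an unadjusted t-test, so adjustment is a bonus and no stated power is at risk. The one shift in weights shows that balance was imperfect for part of enrollment, so the perfect-balance figures overstate the effect. Multiple imputation means that the reported standard errors are not plain sandwich errors. Finally, the list of omitted factors is partly inferred.

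Most of this stands, and it fixes the size of the point: the effect is small, conditional on q and conservative. Two things do not go away. Support person enrollment is named as a balancing factor and appears in no main-effects model. Section 8.0 also relies on further covariates for power while the SAP names only insulin use; the allocation factors are the natural candidates, and adding them costs almost nothing.

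**Conclusion.** The concern holds, as a minor point of precision and transparency. If the omitted factors explain 1% to 10% of the residual variance, the reported standard error is up to 0.5% to 5.4% too large and the nominal 5% test has a true size of 4.9% to 3.9%. Imperfect balance makes the effect smaller. If they explain nothing, there is no effect.

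A positive result would remain valid, the estimates are unbiased and the sample size is unaffected. The conclusion rests on the assumed range for q, on the identity link and on a complete-data calculation at a single time point. It does not carry over directly to the ordinal physical activity model. In support person outcome models enrollment status is constant, so only the patient baselines could matter there.

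**What to change.** - List in the SAP the variables that the randomization algorithm used, and say whether insulin use was one of them.
- Add support person enrollment status (yes/no) and the other listed baselines as covariates in the patient GEE models for continuous outcomes.
- Omit support person enrollment in subgroups where it is constant. The cohabitation moderator, defined as "Whether or not the patient participant and support person live together", yields such a subgroup: patients living with an enrolled support person.
- Leave the ordinal physical activity model as it is, or state that added covariates change the conditional odds ratio being estimated.
- Confirm that both imputation models contain these variables. The SAP describes them only by visit, for example "One imputation model includes baseline, 6- and 9-month data during the intervention", and gives no variable list.
- Parts of the SAP are in the past tense. If the analyses are complete, keep the current model as primary and report the adjusted model as a labelled sensitivity analysis, so that the primary model is not changed after the fact.

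The cost is SAP wording, one list of variables and about three or four degrees of freedom out of 284 to 334 patients (the exact number depends on the list), using data already collected. If the analyses are complete, it is one extra run per continuous patient outcome.

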2.0 Rationale and Specific Aims

We built upon these promising initial findings by expanding and improving FAMS through usability testing and before evaluating FAMS 2.0 in a larger, 15-month randomized control trial (RCT) including support persons (SPs) in both the intervention and control condition. This project's focus aligns closely with the American Diabetes Association's new psychosocial standards and represents an advance in the use of technology to deliver patient and family-centered care. Moreover, this work has the potential to improve the social contexts in which adults live with T2D, key diabetes-related psychosocial outcomes for patients and their family/friends, and glycemic management.

FAMS 2.0 (PI: [name])
R01-DK119292
NCT04347291

The aims of this RCT are:

1. Among patient participants, to evaluate the effects of the expanded FAMS 2.0 intervention versus enhanced treatment as usual (print materials on T2D self-care and access to A1c results) on glycemic management (A1c; primary outcome) and psychosocial well-being (diabetes distress and global well-being; secondary outcomes). We examine effects during the 9-month intervention period and sustained effects after the intervention periods ends.
2. Among support person participants, to explore effects of the expanded FAMS 2.0 intervention versus enhanced treatment as usual (print materials) on psychosocial well-being (diabetes distress) and support burden.
3. To examine intervention effects on intervention targets including:
 - a. Patient participants: family/friend helpful involvement, family/friend harmful involvement, diabetes self-efficacy, and diabetes self-care behaviors
 - b. Support person participants: support person's own involvement in the self-management of the person with diabetes
4. To test hypothesized mediators and explore subgroups difference of intervention effects.

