18.0 Statistical Considerations

This analysis leverages the outcomes measures data already collected during the RCT, including: hemoglobin A1c, diabetes distress, global well-being, self-efficacy, self-care behaviors (dietary behavior, physical activity, medication adherence) and helpful and harmful family/friend involvement.

This analysis leverages engagement data already collected during the RCT, including: enrollment of a support person, text message response rates, coaching session completion rates, elements of coaching protocol including completing rates of goals set, completion of verbal contract to engage friends/family.

The FAMS 2.0 RCT was not designed to test effect modification or moderation by type. Tests of effect modification are exploratory and intended for hypothesis generation, therefore we will interpret patterns of effects and use $p < .10$ as our threshold to discern potentially meaningful differences in intervention effects.

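### Subgroup effects are to be fitted in divided samples, with no planned estimate, interval or test of the difference in effect between subgroups

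*SAP*

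**What the plan says.** Part of Aim 4 (Protocol 2.0) reads: "To test hypothesized mediators and explore subgroups difference of intervention effects". The SAP says that the potential moderators of patient effects "are gender, minority race/ethnicity, socioeconomic disadvantage, and support person cohabitation", and it names gender and cohabitation for support persons.

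The method is one sentence: "We will explore subgroups effects (i.e., divided sample) to determine for whom the intervention was most or least effective using the same models" as those already described. For those models the SAP specifies the following.

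- **Interactions:** "We will allow a two-way interaction between time and condition and a two-way spline interaction between time and baseline value of the outcome".
- **Test:** "Differences between arms will be tested based on a linear combination of regression coefficients at each time point", by a one-degree-of-freedom Wald test.
- **Estimates:** point estimates with 95% confidence intervals at each follow-up, for the difference between arms.

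The only threshold for effect modification is p < .10 in Protocol 18.0. That section belongs to the competing revision and concerns family-functioning type: "The FAMS 2.0 RCT was not designed to test effect modification or moderation by type".

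**The concern.** Saying that an intervention was most or least effective in some group is a statement about the difference between two treatment effects. The plan gives each effect an estimate and an interval, but it has no moderator-by-condition term, no contrast of the subgroup estimates, and no rule for comparing them.

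Readers would then have to judge by eye, either by noting which subgroup reached significance or by ranking the point estimates. Under both habits an effect that is the same in everyone can often look different between groups. At stake is how the moderator results are read and which patients are later described as benefiting most. The primary analysis is not affected.

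**Working it through.** **Inputs.** From Protocol 8.0: A1c difference 0.5 points, SD 1.5, 142 per arm, 5% level (taken as two-sided), 80% power. Assumed, because the documents do not give them: subgroup shares, binary moderators balanced across arms, equal SD in each subgroup, and an adjusted SD of 1.2 as a sensitivity value.

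**The plan's own figure.** SE = 1.5 × √(2/142) = 0.178, and 0.5/0.178 = 2.81, which gives power of 80%. The stated sample size reproduces.

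**If subgroups are compared by within-subgroup significance (assumed rule).** Two-sample t power is p₁ and p₂, with per-arm n = 142 × share. The chance that exactly one subgroup is significant is p₁(1−p₂) + p₂(1−p₁).

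| Uniform effect, SD | Split | p₁, p₂ | Exactly one significant |
|---|---|---|---|
| 0.5, 1.5 | 50/50 | 0.505, 0.505 | 50% |
| 0.5, 1.5 | 40/60 | 0.421, 0.581 | 51% |
| 0.5, 1.5 | 20/80 | 0.235, 0.706 | 61% |
| 0.3, 1.5 | 50/50 to 20/80 | – | 34% to 36% |
| 0.5, 1.2 | 50/50 to 20/80 | – | 42% to 62% |
| 0, any | any | 0.05, 0.05 | 9.5% |

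For equal halves 50% is the maximum, since 2p(1−p) peaks at p = 0.5. An interaction test at 5% would signal falsely 5% of the time for each moderator and time point.

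**Four moderators at one time point.** This was simulated with 284 patients, four independent 50/50 moderators, SD 1.5, and every patient contributing to every moderator. The table gives the chance of at least one discordant pair, against at least one interaction p < 0.05.

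| Uniform effect | Discordant pair | Interaction test |
|---|---|---|
| 0.5 | about 80% | 18–19% |
| 0.3 | 61–63% | 18–19% |
| 0 | about 25% | 18–19% |

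The analytic value for the interaction tests is 1 − 0.95⁴ = 18.5%. With SD 1.2 and a 0.5-point effect, the discordance figure is about 71%.

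**If point estimates are ranked (assumed rule).** The SE of the gap is SD × √(2/n₁ + 2/n₂), with n₁ and n₂ the per-arm subgroup sizes. Under any uniform effect, P(|gap| ≥ x) = 2(1 − Φ(x/SE)).

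| Split, SD | SE | Gap ≥ 0.25 | Gap ≥ 0.5 |
|---|---|---|---|
| 50/50, 1.5 | 1.5 × √(4/71) = 0.356 | 48% | 16% |
| 25/75, 1.5 | 0.411 | 54% | 22% |
| 50/50, 1.2 | 0.285 | 38% | 8% |

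A gap as large as the whole planned effect would thus appear by chance in about one comparison in six at a 50/50 split.

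**Precision of the missing contrast.** The 95% half-width is 1.96 × SE. The difference detectable at 80% power is (1.96 + 0.84) × SE.

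| Split, SD | SE | Half-width | Power for a 0.5 difference | Detectable |
|---|---|---|---|---|
| 50/50, 1.5 | 0.356 | 0.70 | 29% | 1.0 |
| 20/80, 1.5 | 0.445 | 0.87 | 20% | 1.25 |
| 50/50, 1.2 | 0.285 | 0.56 | 42% | 0.8 |

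Cohabitation can be defined only for patients who have a support person, and Protocol 4.0 says that "support person invitation and/or enrollment was not required". If 75% or 50% of patients have one (assumed), the 50/50 SE becomes 0.41 or 0.50.

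**The case against.** The strongest reply is that the gap is small. Every subgroup effect will come with a 95% interval, and the subgroups do not overlap, so a reader can approximate the SE of the difference. The SAP says only that it will explore. It does not say that it will sort subgroups by p-value or rank estimates without their intervals, so the most striking probabilities belong to rules it never states. The models adjust for baseline outcome and insulin use, "which should increase power by reducing the effective standard deviation of the outcome", and a smaller SD lowers several of the figures. The contrast would usually be inconclusive, so it may change little. Finally, the SAP is dated November 2023 and describes some analyses in the past tense, so a change now may amount to a reporting rule more than prespecification.

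Much of this stands. The probabilities illustrate plausible readings and do not predict what the authors will do. The exploratory label limits how serious the point is, and low power is a real drawback.

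None of it supplies the missing quantity. The sentence's stated purpose is to determine where the intervention worked most or least, and leaving readers to derive the difference is not planning to report it. A wide interval tells the reader that the data cannot separate the subgroups, which two side-by-side estimates do not. The rule in Protocol 18.0 does not fill the gap, because it covers another moderator.

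**Conclusion.** The concern holds. For the moderators the SAP names, no estimate, interval or test of the between-subgroup difference is planned, and separate fits with arm contrasts alone do not support the intended conclusion.

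At SD 1.5 with 142 per arm, a uniform 0.5-point effect would look discordant by significance in 50% to 61% of trials for splits from 50/50 to 20/80. At 50/50, a chance gap of at least 0.25 points would arise in 48%. These figures rest on assumed subgroup shares and assumed comparison rules. A lower adjusted SD reduces the gap probabilities, but discordance at 20/80 stays near 62% with SD 1.2. The absence of the contrast depends on none of these assumptions. The point should be addressed, as a matter of how exploratory moderator results are interpreted.

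**What to change.** For each moderator and time point, report the between-subgroup difference in treatment effect with its 95% confidence interval, and make it the basis of any moderator statement. Two routes would serve:

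- keep the divided-sample fits, take the difference of the two estimates within each imputed data set, and pool by Rubin's rules; or
- fit one full-sample GEE with moderator-by-condition-by-time and all lower-order terms, letting the insulin and baseline-spline effects vary by subgroup if wanted.

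Keep the subgroup-specific estimates as description and label the contrasts exploratory. State the levels compared for each moderator and that patient cohabitation applies only where a support person enrolled. Confirm that the imputation model allows the effect to differ by moderator, since the SAP does not list its terms. If the subgroup analysis has already been run, add the contrast to the report and say when it was added.

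The cost is SAP wording and one contrast per moderator and time point, with no new data and no change to the primary analysis. The drawback is imprecision: many contrasts will be inconclusive, and the text should say so in advance.
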